## 3. Definitions

## 3.1. Dates and Points of Reference

• Study Day 1: the date of the first dose of study treatment in 232SM203

Note: Efficacy sets defined as subjects with the opportunity to attend the visit if the study had not stopped due to efficacy.

- Study Day
  - $\circ$  For a date on or after Study Day 1

Study Day = (Date of Interest) - (Study Day 1) + 1

o For a date before Study Day 1

Study Day = (Date of Interest) – (Study Day 1)

In order to distinguish nominal visit names from duration defined in days, visit names will be referred to as "Day 15", "Day 29", etc., and "15 days" or "29 days", etc. will be used to define time intervals.

Overall time on study will be defined as the total number of days a participant is known to be followed on study calculated as follows:

Overall time on Study = (Last date on study) – (Date of first dose) +1

Last date on study is defined as the date of the latest visit or evaluation or telephone contact, or time of death from all available data for a given participant.

Disease duration is defined as time from age at symptom onset to age at informed consent.

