# 6. Efficacy Endpoints

## 6.1. General Analysis Methods for Efficacy Endpoints

## **Multiple imputation (MI)**

Product: Nusinersen	Statistical Analysis Plan
Study: 232SM203	Version: 3.0 Final

The multiple imputation method [Schafer 1997, Schafer 1999] will be used for participants who discontinue for a reason other than death or have a missing efficacy result at the timepoint of interest. This will be performed for CHOP INTEND, HINE Section 2 total score and NF-L. Any imputation on an item level within a scale for CHOP INTEND and HINE section 2 will be performed prior to performing MI.

The imputations will be performed on total scores. All available data will be used i.e., where subjects have missed doses but continued to perform assessments; otherwise, any missing values will be imputed using MI. In a situation where historical data is used as the control group only the visits which are common between the two groups will be utilized. For example, for the CS3B sham control versus higher dose comparison only the Day 64, Day 183 and Day 302 visits will be included in the list of post baseline visits.

In this situation if convergence issues occur then only the Day 64 and Day 183 post baseline visits will be included.

The Markov Chain Monte Carlo (MCMC) method will be used to impute the missing score.

The treatment variable will be coded so that the Higher dose group is the first in the sort order. Prior to the Proc MI step the dataset will be sorted by treatment and then ascending unique subject identifier (USUBJID). The variable list in the model for imputations will include:

- treatment group, disease duration, baseline value for the endpoint, and all available post baseline values
- For NF-L, the log of baseline and post-baseline values will be used in the PROC MI step.

A set of 100 complete imputed datasets will be generated and the relative efficiency parameter will also be checked to determine the acceptability of the imputed results i.e. it should be close to 98% or higher. The seed used for the multiple imputation for CHOP INTEND will be 5846892, for HINE section 2 Motor Milestones will be 8746890 and for NF-L will be 7635789.

If the MI procedure imputes any values outside the expected range for the scale, e.g. from 0 to 64 for CHOP INTEND, then values below 0 will be set to 0 and values above 64 will be set to be 64. For NF-L if any imputed values are  $< \log(LLOQ)$  then set as  $\log(LLOQ/2)$ .

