## Joint rank methodology

Death is a potential outcome in the infantile-onset population and the joint rank methodology will be utilized to incorporate both the functional endpoint and mortality.

The joint rank methodology [Berry 2013] allows for a statistical test of the treatment effect on the endpoint while accounting for truncation of data due to deaths. In this analysis, a subject's joint rank score will be calculated by comparing each subject to every other subject in the study, resulting in a score of +1 if the outcome was better than the subject being compared, -1 if worse, and 0 if the same. The subject's score will then be calculated by summing their comparison to all the other subjects in the study.

For the purpose of this calculation, considering an endpoint for change to Day 183, subjects will be grouped into the following 2 categories:

- Group 1: Participants who complete Day 183 and have data available AND subjects who withdraw from the study due to reasons other than death and don't have Day 183 data available
- Group 2: Participants who die will be ranked based on the time of death

The criteria for withdrawals are based on withdrawal from study. A subject may discontinue treatment but still continue in the study and in this case data from assessments conducted after treatment will be included for analysis.

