### 6.6.5. Proportion of Time on Ventilation

The ventilation use during the study will also be collected via the daily ventilation diary. Daily ventilation use data that are missing will be imputed using the greater of the days that flank the missing day(s).

For each subject, the total number of hours of ventilation support required during the study will be calculated and prorated according to number of days on study. Based on the prorated number of hours of ventilation support, treatment groups will be compared via an analysis of covariance adjusting for each subject's disease duration at Screening and baseline CHOP INTEND total score.

An additional analysis of the number of days in which each subject required ventilation support of  $\geq 16$  hours per day will be performed. The number of days that this level of ventilation was required will be analyzed by analysis of covariance adjusting for each subject's disease duration at Screening and baseline CHOP INTEND total score.

Analyses will be performed on the ITT Set.

Product: Nusinersen	Statistical Analysis Plan
Study: 232SM203	Version: 3.0 Fina

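### Days at 16 or more hours of ventilation are compared as a raw count, so an arm with more early deaths or shorter follow-up can look better; use the proportion of days on study

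*SAP*

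**What the plan says.** All references are to the Part B infantile-onset SAP. Section 2.1 lists the endpoint as a proportion of time on ventilation, and Section 6.6.5 carries that title. It holds two between-arm analyses on the ITT Set:

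- **Hours.** For each infant, "the total number of hours of ventilation support required during the study will be calculated and prorated according to number of days on study". The prorated value is compared by ANCOVA.
- **Days.** A further analysis takes each infant's days at 16 or more hours: "The number of days that this level of ventilation was required will be analyzed by analysis of covariance". The only covariates named are disease duration and baseline CHOP INTEND. No denominator, offset, or rule for death or withdrawal is stated for this count.

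Three other provisions bear on it:

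- Missing diary days take the greater of the two flanking days (Section 6.6.5).
- "Last date on study is defined as the date of the latest visit or evaluation or telephone contact, or time of death" (Section 3.1), so time on study ends at death.
- On multiple imputation, Section 6.1 says: "This will be performed for CHOP INTEND, HINE Section 2 total score and NF-L". Ventilation days are not included.

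**The concern.** A count of days depends on how long the infant is observed. An infant who reaches 16 hours a day and dies soon after contributes few days; one who reaches it on the same day and survives contributes many. With equal ventilation need in both arms, the arm with more early deaths then has the lower mean, which reads as less burden. Early withdrawal has the same effect.

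The plan is aware of the problem: "Death is a potential outcome in the infantile-onset population", and the functional scores use a joint rank for that reason. It also scales the neighbouring outcomes to time on study. Hospital days are prorated and hospitalisation counts carry a log-time offset (Section 6.6.2), as do serious respiratory events (Section 6.6.4). The day count is the exception, under a heading that promises a proportion.

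At stake is the reading of one supportive comparison of 50/28 mg with 12 mg. If the higher dose improves survival, as the sample-size section assumes, the raw count tends to work against it. If survival were worse, the count could mask part of the harm.

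**Working it through.** The SAP gives no expected value or power for this outcome, so there is no plan figure to reproduce.

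**1. Does anything in the plan repair the count?** No. The flanking-day rule needs a later observed day, so it cannot fill days after death. Multiple imputation does not cover this outcome. The covariates include neither time on study nor death.

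**2. One infant.** Assume 16 hours a day from Day 60, with days counted inclusively.

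- Alive to Day 302: 302 − 60 + 1 = 243 days; 243/302 = 0.80 of time on study.
- Dead on Day 90: 90 − 60 + 1 = 31 days; 31/90 = 0.34 of time on study.

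The raw gap is 212 days. Proration narrows it but does not close it.

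**3. Arm level at the plan's survival difference.** From the SAP: an additional 3% survival over 12 mg (Section 2.3). Assumed: 30% of each arm ventilated from Day 60, with all deaths at Day 90 among them.

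- Raw count: 0.03 × (243 − 31) = 6.4 days, which is 6.4/302 = 2.1% of the period.
- Prorated: 0.03 × (0.805 − 0.344) = 0.014, or 1.4 percentage points of time on study.

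**4. Less extreme timing.** A simulation of 400,000 infants per scenario assumed the same ventilation need throughout: 30% ventilated, onset uniform over Days 1–200, deaths uniform over Days 20–180.

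| Deaths | Mean raw days, 3% to 30% dead | Per point of deaths | At 3 points | Mean prorated share |
|---|---|---|---|---|
| Unrelated to ventilation | 59.2 to 45.2 | 14.0/27 = 0.52 | 1.6 days | 0.197 to 0.163 |
| Only among ventilated infants | 55.5 to 9.1 | 46.4/27 = 1.72 | 5.2 days | 0.188 to 0.075 |

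Steps 3 and 4 together give about 2 to 6 days.

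**5. A larger gap, to see what each remedy does.** In the set-up of step 3, take deaths of 8% v 20% (a 12-point gap that the plan does not assume).

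- Raw: 0.08 × 31 + 0.22 × 243 = 55.9 days v 0.20 × 31 + 0.10 × 243 = 30.5 days.
- Prorated: 0.08 × 0.344 + 0.22 × 0.805 = 20% v 0.20 × 0.344 + 0.10 × 0.805 = 15%.
- Fixed period to Day 302, days after death counted as 16-hour days: 0.30 × 243/302 = 24% in both arms.

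**6. Can the direction reverse?** Yes. If the extra deaths are infants who would otherwise never have been ventilated, each after 5 to 60 days at 16 hours, 3 points of extra deaths add 0.03 × 5 = 0.15 to 0.03 × 60 = 1.8 days. The arm with more deaths then looks worse. At 20 points the addition is 1 to 12 days.

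**7. Follow-up among survivors.** Section 3.3 allows 23 to 120 days of follow-up. If the diary runs through it, two infants ventilated from the same day can differ by 120 − 23 = 97 counted days through scheduling alone. Between randomised arms this is mainly noise, and a denominator largely removes it.

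**The case against.** The strongest reply has four parts.

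- **Size.** In step 3 with 8% v 11% deaths, the SDs are about 100 and 94 days. With 50 and 25 infants the SE of the difference is √(100²/50 + 94²/25) = 23.5 days. A shift of 6.4 days is about a quarter of one SE. This stands.
- **Direction.** If the dose improves survival, the bias tends to run against 50/28 mg and does not manufacture a benefit. This stands for that scenario.
- **Death is covered elsewhere.** For this comparison, time to death or permanent ventilation and time to death are ranks 10 and 11 of the testing sequence, and sensitivity joint-rank analyses of the functional scores rank death and permanent ventilation lowest. This stands, and it limits the consequence. It does not make the day count interpretable by itself.
- **Remedy.** Proration leaves 20% v 15% in step 5, and the prorated hours analysis is also cut short by death. Counting days after death as ventilated days changes the quantity from ventilation burden to a death-or-ventilation composite; in step 5 it returns equal arms despite a 12-point mortality gap. This is why the composite belongs in a sensitivity analysis. The missing denominator remains a departure from the plan's own practice.

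A reader might infer that the arm with more deaths must look better, or that the comparison is off by some 25 days. The documents support neither: step 6 reverses the sign, and 25 days needs a 12-point mortality gap where the plan assumes 3.

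**Conclusion.** The point holds as a tendency. The day count has no allowance for time on study, although hours in the same section do and the endpoint is named a proportion of time. An arm with more early deaths or shorter follow-up can look better, by about 2 to 6 days at the plan's 3-point survival difference. That range rests on assumptions outside the SAP: 30% of infants reaching 16 hours a day, equal need in both arms, and the onset and death timings above. The sign depends on whether the extra deaths fall among infants already ventilated or follow new, long ventilation.

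The weight is low. It would be tempting to read this as a threat to the trial's efficacy conclusions, but the SAP presents it as an additional analysis of a remaining secondary endpoint, outside the 11-step sequence, so no confirmatory conclusion depends on it.

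**What to change.** In Section 6.6.5, replace the raw count with the proportion of days on study on which the infant needed at least 16 hours of ventilation, keeping the same ANCOVA and covariates. Numerator and denominator should cover the same days. This follows the plan's practice for ventilation hours and hospital time.

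Add one sensitivity analysis over a fixed period from first dose to Day 302, in which days after death count as days at 16 or more hours. State the rule for infants who leave alive before Day 302, for example proration over their observed days. Say that both results are to be read beside time to death or permanent ventilation for the same comparison.

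The cost is a sentence or two in the SAP and one extra model run on data already collected. The sensitivity analysis answers a different question, about ventilation or death combined, so it should be labelled as such and should not replace the main one.

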### 6.6.6. Ventilator Use

The participant's ventilator use and respiratory aids will be collected at every study visit

The ventilation use will be summarized by visit and listed.

### 6.6.7. Change in the Parent Assessment of Swallowing Ability Scale (PASA)

Parent Assessment of Swallowing Ability (PASA) Dysphagia will be assessed using the PASA questionnaire. Caregivers will be asked a series of questions regarding the mealtime behavior of the participant.

The PASA questionnaire was developed by a Biogen team in order to assess the signs and symptoms of dysphagia. This questionnaire consists of 33 items across 4 domains that cover general feeding, drinking liquids, eating solid foods, and assessment of swallowing concerns. The first 3 of these domains are generally assessed with 5 levels of response (Never, Rarely, Sometimes, Often, and Always), although 2 items are assessed with a simple "Yes"/"No" answer. In the final domain, the assessment of swallowing concerns has 4 levels of response: Strongly Agree, Agree, Disagree, and Strongly Disagree. In answering each item, the caregiver is directed to consider the previous 7 days.

The number, mean score, and percentage of subjects scoring each category in the PASA Section 1 -General Feeding will be presented by visit. In addition, a stacked bar chart will be used to summarize the proportion of subjects in each category over time for each item. Depending on the number of subjects who complete PASA Sections 1,2, 3, and 4, similar presentations may also be made or alternatively the results from these visits will be listed.

### 7. Safety Endpoints

### 7.1.1. Adverse events

The analysis of safety will be performed using the respective Safety Sets and presenting by 232SM203 treatment groups. The sham participants from safety sets from CS3B will be included for the analysis of adverse events.

All AEs will be analyzed based on the principle of treatment emergence where treatment emergence will be relative to the first dose of nusinersen. An AE will be regarded as treatmentemergent if it was present prior to receiving the first dose of nusinersen and subsequently worsened in severity or was not present prior to receiving the first dose of nusinersen but subsequently appear. Refer to Appendix A for more details about AE with missing start or stop dates.

A participant having the same AE preferred term more than once will be counted only once in the incidence for that event. Multiple occurrences of the same adverse event for the same subject will all be counted in the frequency for that adverse event.

Product: Nusinersen	Statistical Analysis Plan
Study: 232SM203	Version: 3.0 Final

The occurrence of the AE with the greatest severity will be used in the calculation of incidence by severity. The AE relationship to treatment or LP/sham procedure is captured as related or not related. In the event the relationship is missing then this will be considered related.

Due to the long half-life of nusinersen, analyses of treatment-emergent adverse events will include all events reported during the study. Adverse Events will be coded using the Medical Dictionary for Regulatory Activities.

The following presentations will be shown:

an overall summary showing, for each treatment group, the number and percentage of subjects with an adverse event, a mild, moderate or severe event, an event related to study drug, an event related to lumbar puncture /sham procedure, a serious event, a serious event related to study drug, an event leading to study drug withdrawal, an event leading to study withdrawal, and a fatal event.

incidence and frequency by system organ class and preferred term

incidence and frequency by preferred term

incidence and frequency, by preferred term, in at least 5% of subjects in any treatment group

incidence of adverse events by maximum severity by preferred term

incidence and frequency of severe events by system organ class and preferred term

incidence and frequency of events related to study drug by system organ class and preferred term

incidence and frequency of events related to lumbar puncture /sham procedure (as assessed by the investigator) by system organ class and preferred term

incidence by system organ class and preferred term that occurred within 24 hours of Dosing or Sham Procedure

incidence by system organ class and preferred term that occurred within 72 hours of Dosing or Sham Procedure

incidence and frequency of serious adverse events by system organ class and preferred term

incidence and frequency of serious adverse events related to study drug by system organ class and preferred term

incidence of events that led to fatal outcome

incidence of events leading to study drug withdrawal by system organ class and preferred term incidence of events leading to withdrawal from study by system organ class and preferred term incidence and frequency of adverse events over time by system organ class and preferred term.

Product: Nusinersen	Statistical Analysis Plan
Study: 232SM203	Version: 3.0 Final

incidence and frequency of adverse events antibody status by system organ class and preferred term.

A separate table will also be presented to show an overall summary of COVID-19 pandemic related AEs.

Listings of the following events will be produced.

AEs

SAEs

AE with fatal outcome

AEs led to study drug withdrawal

AEs led to withdrawal from study

AEs related to lumbar puncture/sham procedure

AEs related to study drug

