## Summary of How Historical Data Will be Used in the Analysis

The enrollment criteria of the Part B infantile-onset in 232SM203 has been designed to be similar to CS3B study (external data). In general, consistent inclusion/exclusion criteria have been utilized and efficacy assessments at the same timepoints have been included.

As part of the analysis of the 232SM203 study the external data will be utilized for the following purposes:

- For the primary and secondary endpoints comparing to sham, the higher dose participants from 232SM203 will be compared to matched sham control participants from CS3B. Comparability will be assessed for 232SM203 compared to CS3B sham based on key covariates and a matching algorithm will be utilized to select at least 20 CS3B sham control subjects. For the remaining secondary endpoints, the high dose participants will be compared to 12 mg dose using the 232SM203 ITT population.
- Use of the group of matched control subjects described in the first bullet for summaries of safety endpoints. This is in order to provide a reference group of participants with similar disease who have not undergone lumbar puncture SMA.

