#### ii Concomitant Therapy and Procedure

In order to define concomitant therapies with missing start or stop dates, the following additional criteria will be used:

- If both the start and stop dates of a particular therapy were missing, that therapy is considered concomitant.
- If the start date of a therapy was missing and the stop date of that therapy fell on or after the date of dosing, that therapy is considered concomitant.
- If the start date of a therapy was prior to the date of dosing and the stop date of that therapy was missing and the therapy was listed as continuing, that therapy is considered concomitant.
- If the start date of a therapy was prior to the date of dosing and the stop date of that therapy was missing and the therapy was listed as *not* continuing, that therapy is considered concomitant.
- If the start/stop date of a therapy is partial then where it is not possible to rule out that it was not taken concomitantly it will be considered concomitant.

Denote the end date of medications as CMENDT and the study treatment start date as TRTSTDT. The medication is classified concomitant provided any of the following is NOT true:

- CMENDT is complete and CMENDT is less than TRTSTDT.
- Day of CMENDT missing and year/month of CMENDT is strictly before year-month of TRTSTDT.

• Month of CMENDT is missing and year of CMENDT is strictly before year of TRTSTDT.

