# 2.4.2.CS11 Study

This was an open-label extension study in participants with SMA who previously participated in investigational studies of nusinersen. The last participant completed the study on 21Aug2023. The primary purpose of this study was to gather additional information on the long-term safety, tolerability, and efficacy of repeated doses of nusinersen. Participants who were randomized to receive sham control in CS4 switched to receive 12 mg nusinersen at the start of CS11, so this dataset provides additional patients who were naïve to treatment.

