# 6. Safety Endpoints

The analysis of safety will be performed using the Safety Set. The main analysis will be to compare the two arms of 232SM203. Presentations will also be included for AEs, SAEs and related AEs comparing sham from the matched CS4 Sham to the 232SM203 higher dose arm.

AEs will be analyzed based on the principle of treatment emergence where treatment emergence will be relative to the first dose of nusinersen. An AE will be regarded as treatment-emergent if it was present prior to receiving the first dose of nusinersen and subsequently worsened in severity or was not present prior to receiving the first dose of nusinersen but subsequently appear. Refer to Appendix A for more details about AE with missing start or stop dates.

A participant having the same AE preferred term more than once will be counted only once in the incidence for that event. Multiple occurrences of the same adverse event for the same subject will all be counted in the frequency for that adverse event.

Product: Nusinersen	Statistical Analysis Plan
Study: 232SM203	Version: 1.0

The occurrence of the AE with the greatest severity will be used in the calculation of incidence by severity. The AE relationship to treatment or LP/sham procedure is captured as related or not related. In the event the relationship is missing then this will be considered related.

Due to the long half-life of nusinersen, analyses of treatment-emergent adverse events will include all events reported during the study. Adverse Events will be coded using the Medical Dictionary for Regulatory Activities.

The following presentations will be shown:

- an overall summary showing, for each treatment group, the number and percentage of subjects with an adverse event, a mild, moderate or severe event, an event related to study drug, an event related to lumbar puncture /sham procedure, a serious event, a serious event related to study drug, an event leading to study drug withdrawal, an event leading to study withdrawal, and a fatal event.
- incidence and frequency by system organ class and preferred term
- incidence and frequency by preferred term
- incidence and frequency, by preferred term, in at least 2 subjects in any treatment group
- incidence of adverse events by maximum severity by preferred term
- incidence and frequency of severe events by system organ class and preferred term
- incidence and frequency of events related to study drug by system organ class and preferred term

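### Part B ties treatment emergence to a nusinersen dose that sham controls did not receive in CS3B or CS4, the infantile-onset SAP names two sham AE populations, and the concomitant-medication rule in all four SAPs is always met

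*SAP*

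**What the plan says.** **Treatment emergence.** In the Part B infantile-onset SAP, Section 7.1.1, "All AEs will be analyzed based on the principle of treatment emergence", where "treatment emergence will be relative to the first dose of nusinersen", and a new event qualifies if it "was not present prior to receiving the first dose of nusinersen but subsequently appear". The same section states: "The sham participants from safety sets from CS3B will be included for the analysis of adverse events". Section 2.4 describes the CS3B control arm as having had a sham procedure. The later-onset SAP, Section 6, uses the same nusinersen anchor and plans displays of AEs, SAEs and related AEs "comparing sham from the matched CS4 Sham to the 232SM203 higher dose arm". Its Section 2.4.2 explains: "Participants who were randomized to receive sham control in CS4 switched to receive 12 mg nusinersen at the start of CS11".

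**Sham population.** Section 7.1.1 of the infantile-onset SAP takes sham participants from the CS3B safety sets. Section 2.4 of the same SAP plans "Use of the group of matched control subjects described in the first bullet for summaries of safety endpoints", and Section 3.2 puts matched CS3B sham beside 50/28 mg for key adverse event displays.

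**Concomitant therapy.** The infantile-onset Appendix A states: "The medication is classified concomitant provided any of the following is NOT true". Three conditions on the end date follow: (1) it is complete and earlier than treatment start; (2) the day is missing and the year-month is earlier; (3) the month is missing and the year is earlier. The same rule stands in Part A Section 5.1, in the later-onset Appendix A and in the Part C Appendix A. The main text of each SAP (Part A 5.5, infantile-onset 7.1.2, later-onset 6.1.1, Part C 5.5) defines a concomitant therapy as one taken on or after the first injection, including earlier therapies only if they continued.

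**The concern.** The sham column is there, according to Section 2.4 of the infantile-onset SAP, as a reference group with similar disease and no lumbar puncture. A reference column needs a start date for counting events and one denominator. The SAP gives no start date that exists for these participants, and it gives two denominators. If the rule is followed, the column is blank. If it is not, the programmer chooses the anchor and the population for historical data whose results are already known.

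The concomitant rule is a separate matter with the same character: an operative rule that, if followed, contradicts the definition it is meant to implement. Prior medication would be mixed into the concomitant tables.

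**Working it through.** The plan states no figure to reproduce here, so the check is mainly logical.

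**1. Treatment emergence for sham controls**

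- CS3B sham: no nusinersen in the study, so no first-dose date exists. Neither limb of the definition (worsening after that dose, or appearing after it) can be met.
- CS4 sham: first nusinersen is at the start of CS11. Every event of the CS4 sham period therefore precedes the anchor.
- Appendix A of each Part B SAP refers to the start of study treatment for missing and partial dates, but does not set this to the first sham procedure. Section 2.2 of the infantile-onset SAP lists study treatment administration and sham procedure as separate things, and Section 7.1.1 names the sham procedure explicitly for the 24-hour and 72-hour windows.
- The follow-up adjusted incidence rates in both Part B SAPs count time from the first dose, so the sham person-time has the same gap.
- Intent is visible. The notes on severity and seriousness in CS3B and CS4 treat records from those studies as able to be treatment emergent, and Section 3.2 of both Part B SAPs plans a sham AE column.

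**2. Sham denominator (infantile-onset)**

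- Matched controls: a subset of 37 (Table 1), with a floor of 20 (Section 6.2).
- CS3B sham safety set: its size is not legible in the text. Assuming that 122 randomized 2:1 split exactly, 122 / 3 = 40.7, about 41.
- Ratio of the two candidates: 41 / 37 = 1.1 up to 41 / 20 = 2.05.

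**3. Concomitant rule**

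- If the end date is complete, conditions 2 and 3 are false.
- If any part of it is missing, condition 1 is false.
- So at least one condition is always false, and a rule that asks only for one untrue condition is always met.

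This was checked by enumeration, with an assumed first dose on 15 June 2021 and end dates built from year 2020, 2021, 2022 or missing (4), month 1 to 12 or missing (13) and day 1 to 28 or missing (29):

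- Patterns: 4 × 13 × 29 = 1,508.
- Rule as written: 1,508 of 1,508 concomitant.
- Rule requiring that none of the three be true: 972 concomitant and 1,508 − 972 = 536 prior only.
- Breakdown of the 536: complete earlier dates 12 × 28 + 5 × 28 + 14 = 490; day missing with an earlier year-month 12 + 5 = 17; month missing with an earlier year 29. Sum: 490 + 17 + 29 = 536.

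At most one condition is true at a time on a strict reading of condition 2. On a loose reading, where a year-only date may satisfy it, two can be true together. The result is 1,508 of 1,508 either way. These counts show the logic and do not estimate how many trial medications are affected.

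**The case against.** The best reply is that intent is plain and any programmer would follow it. The CS3B and CS4 notes presuppose treatment-emergent sham events. The infantile-onset SAP also uses first dose loosely for sham participants elsewhere, for example as the start of time to death or permanent ventilation in Section 6.4.7. Section 7.1.1 adds that all events reported during the study are included. This shows what was meant, but it does not supply the date: Section 7.1.1 and later-onset Section 6 name nusinersen, and including all reported events does not say where counting starts.

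On the sham population, Section 3.2 speaks only of key AE displays, so it could stand beside a wider set in Section 7.1.1. Section 2.4, however, assigns the matched controls to safety summaries generally, so the conflict remains.

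On concomitant therapy, the main-text definition is correct, and the appendix rule is introduced as additional criteria for missing dates. But its first condition concerns complete end dates, so the rule is not confined to missing ones.

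Three stronger inferences are tempting, and the documents do not support them:

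- *The 50/28 mg arm will look worse by construction.* Sham incidence is better called undefined than truly zero, the intent to count sham events is evident, and a blank column would be noticed. The comparison of the two 232SM203 arms is unaffected.
- *At least two of the three conditions always fail.* A year-only end date can satisfy conditions 2 and 3 together on the loose reading. Only at least one is certain, and that is enough.
- *The Matched Sham Set is the right AE population.* Table 1 defines that set to include the higher-dose ITT participants, which would move the 50/28 mg arm from as-treated to as-randomized.

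**Conclusion.** The point holds as a set of wording errors in operative rules.

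- In both Part B SAPs, no sham event can be classed as treatment emergent if the text is followed. This rests on CS3B and CS4 sham participants having received no nusinersen within those studies, which the SAPs state or directly imply.
- In the infantile-onset SAP, the sham AE denominator is unsettled between 20 to 37 matched controls and roughly 41 (assumed from the 2:1 allocation).
- In all four SAPs, the concomitant rule excludes nothing and contradicts the main-text definition.

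The reach is limited to descriptive safety and concomitant-therapy displays. No efficacy result changes, the 12 mg versus 50/28 mg AE comparison does not depend on the sham anchor, and Parts A and C are touched only by the concomitant rule. It should be corrected before the tables are programmed.

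**What to change.** 1. In infantile-onset Section 7.1.1 and later-onset Section 6, define treatment emergence from the first nusinersen dose in 232SM203 or, for sham controls, from the first sham procedure in CS3B or CS4, ending before any CS11 dose. Use the same start for the follow-up adjusted incidence rates.
2. In infantile-onset Section 7.1.1, name the matched CS3B sham controls alone as the AE reference group, in line with Sections 2.4 and 3.2, and state that the 232SM203 arms stay on the as-treated Safety Set. Do not cite the Matched Sham Set label for this.
3. In Part A Section 5.1 and in Appendix A of the two Part B SAPs and the Part C SAP, reword the rule so that a medication is concomitant provided none of the three conditions is true.

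The cost is SAP wording only. No new data, sample size change or efficacy re-analysis is needed.
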